The disadvantages accompanied with the use of the conventional surgical method of caries removal has been overcome by the use of “chemo-mechanical caries removal method”. “Chemo-mechanical caries removal” is one of the minimally invasive techniques that found to be less painful, less destructive and more accepted by children (Goomer et al., 2013, Soni et al., 2015). In addition to these advantages, the research holds clinical significance as a novel agent for “chemo-mechanical caries removal” (BRIX3000[®]) by the laboratory Brix Medical Science. It has been released recently in the dental market in 2015. It is a papain-based gel derived from leaves latex and fruits of green papaya (Carcia Papaya) that works as chemical debridement. It is for atraumatic caries removal with unique technology Encapsulating Buffer Emulsion (EPE) (Felizardo et al., 2018). This technology, according to the manufacture, provides the product with:

1. Proteolytic enzymatic activity that differs than previous products (Carie-Care) in the amount of papain used (3,000 U/mg in a concentration of 10%).
2. Perfect pH that solidifies the enzymes and set them free instantly on the collagen through its proteolytic activity.
3. Stable in room temperature with no need to be refrigerated with increased its shelf-life up to 48 months.
4. Increased enzymatic selectivity to damaged collagen.
5. Reduced time needed for removing the damaged dentinal tissues.
6. Enhanced the antifungal, antibacterial, and antiseptic ability.
7. Increased roughness to the cavity floor that favored better adhesion of the restoration.

By reviewing the literature, there are limited studies concerning its implementation in the area of pediatric dentistry. Clinical and microbiological studies are needed to confirm

manufacturer's claims by comparing this novel chemo-mechanical agent (BRIX3000[®]) and the previously-available chemo-mechanical agent (Carie-Care[™]) to the conventional surgical method for caries removal. Therefore, the purpose of this research is to perform clinical and microbiological evaluation of caries removal using these three different methods of caries removal in primary molars.

RESEARCH OBJECTIVES

- 1) To compare the efficacy of the chemo-mechanical method (BRIX3000[®], Carie-Care[™]) versus the conventional surgical method in decreasing the cariogenic bacteria in dentine caries of primary molar teeth in vivo.

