- 2) To compare the efficiency of the chemo-mechanical method (BRIX3000[®], Carie-Care[™]) versus the conventional surgical method in caries removal of primary molar teeth in vivo.
- 3) To compare the pain experienced by children during dental treatment with the chemo-mechanical method (BRIX3000[®], Carie-Care[™]) versus the conventional surgical method in caries removal of primary molar teeth in vivo.

HYPOTHESIS

The null hypothesis for this research will be as follows:

There is no difference in the efficacy, efficiency and pain experienced between chemo-mechanical caries removal agents (Brix3000[®]), (Carie-CareTM) and the conventional surgical methods in primary molars.

RESEARCH MATERIALS AND METHODS

This study will be carried out at King Abdulaziz Dental University Hospital (KADUH) and at Microbiology Research Laboratory in the Faculty of Pharmacy, King Abdulaziz University in Jeddah, Saudi Arabia to evaluate the efficacy, efficiency, pain experienced by children with the use of the chemo-mechanical method (BRIX3000[®]) and (Carie-Care[™]) versus the conventional surgical method in primary molars.

Materials:

Ethical Approval

The study was approved by the “Research Ethics Committee” at Faculty of Dentistry, King Abdulaziz University (KAU), under approval number 107-06-19.

Informed Consent

Written informed consent will be received from the parents or the guardians of the children after explaining the research procedures to them.

Subjects (sampling)

The study sample will consist of healthy and cooperative children between the ages of 4-9 years with bilateral open occlusal carious lesions in primary molars, who will attend as outpatients to the Department of Pediatric Dentistry at KADUH during the period from October 2019 to October 2020.

Inclusion criteria:

- Healthy and cooperative patients of age group 4-9 years.
- Primary first/second molars with open occlusal carious lesion having moderated depth and clinically visible brownish color softened dentin.
- No clinical signs or symptoms of pulp degeneration, such as tenderness to percussion and history of sinus tracts or swelling. Intraoral periapical radiographs with lesions having radiolucency extending into, but only confined to dentin.

Exclusion Criteria:

- Patients with any major and minor systemic illness.
- Uncooperative patients that necessitate pharmacological dental treatment.

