- 9) Inoculation loop.
- 10) Blood agar plates “Schaedler agar”
- 11) GC Fuji IX GP®.
- 12) A Stop Watch.

Methods:

Study design

Experimental, randomized controlled clinical trial with two-arm parallel groups and bilateral design following the “Consolidated Standards of Reporting Trials (CONSORT,2010)” statement (Fig.3).

Randomization

Since bilateral technique will be utilized in both parallel groups, it was decided to start on the right side irrespective of the method assigned by randomization. To control the variable of the side favored by the clinician, the researchers will make sure that each side is treated evenly by both methods using block randomization. Before recruiting participants, 60 sealed envelopes containing the randomization results will be arranged, sealed and mixed blindly in a box. Each envelope represents a block of the two contralateral teeth. The envelopes will be numbered blindly from 1 to 60. Each envelope will be opened immediately before starting the procedure on the right side.

[figure not shown]

Figure 3: Flow diagram of the Study

Clinical Procedures

The degree of dental destruction will be clinically determined by using a dental probe. Only open occlusal cavities with brown and softened dentin with broadly comparable depth exhibiting frank moderate cavitation will be chosen “severe decay, stage 5, ICDAS [International Caries Detection and Assessment System]” (Ismail et al., 2007, Dikmen, 2015). The depth of caries progression will be confirmed with an intraoral periapical radiograph such that radiolucency did not involve the pulp.

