To assess the efficacy of caries removal in all groups, the outer surface of the decayed lesion will be washed with sterile normal saline (5 mL) to avoid contamination of plaque bacteria before taking the sample. The first sample will be taken from superficial carious lesion with the aid of a sterile sharp spoon excavator (Size #4; Nordan Manufacturing Inc., [name]). After completing caries removal, the cavity will be washed with sterile normal saline (5 mL) and dried with a sterile cotton pellet. A second sample of dentin will be taken from different sites of the cavity including the walls and floor using a sterile sharp spoon excavator (Size #4; Nordan Manufacturing Inc., [name]). The first and second samples will be collected in screw cap sterile vials containing 1 ml of isotonic saline for microbiological evaluation. Following decay elimination by both techniques, cavities will be filled using Glass Ionomer restoration (GC Fuji IX GP[®]) according to manufacturer’s instructions. For Microbiological cultivation and evaluation, dentin samples of all groups will be processed in the Advanced Techniques Laboratory in Dental research within 2 hours of collection. The samples will be vortexed for 30 sec to remove the microorganisms from dentin. The samples will be then regularly watered to obtain a 10^4 , and a sterile loop full of sample (0.1 ml) will be collected and cultured with aseptic technique onto blood agar plates (Schaedler agar) by streaking method. Then, the plates will be incubated aerobically at 35°C for 24 hours. Using

colony counter, the total viable count (TVC) will be obtained and expressed as colony forming units “CFU” per ml of sample.

To determine the efficiency of caries removal in all groups, time will be recorded in seconds by using a stopwatch from the beginning of caries removal till the cavity is certain to be caries-free.

To assess the pain experienced throughout caries removal in all groups, the “Wong-Baker FACES® Pain Rating Scale” (Wong & Baker, 1988) will be utilized (Fig. 4).

Dental treatment will be accomplished according to the following steps:

- Local anesthesia will be used for all groups.
- Rubber dam isolation will be used for all groups.
- Caries removal will be done utilizing one of the 3 techniques as follows:

The Control Group: Caries removal using “conventional drilling method”

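### Objective 1 concerns cariogenic bacteria, but the plan counts only total aerobic viable bacteria, so the organism-specific inference is not supported as written

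*Combined protocol and SAP*

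**What the plan says.** All places are in the combined protocol and SAP.

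- **Research Objectives, item 1.** The chemo-mechanical agents are to be compared with conventional drilling "in decreasing the cariogenic bacteria in dentine caries of primary molar teeth in vivo".
- **Hypothesis.** The null hypothesis speaks of efficacy, not of any organism: "There is no difference in the efficacy, efficiency and pain experienced between chemo-mechanical caries removal agents" and the conventional methods.
- **Clinical Procedures.** The microbiological sampling is introduced with "To assess the efficacy of caries removal in all groups". One dentin sample is taken before caries removal and one after. Both are "cultured with aseptic technique onto blood agar plates (Schaedler agar) by streaking method". The next step is "Then, the plates will be incubated aerobically at 35°C for 24 hours". The result is the total viable count, per ml of sample: "colony counter, the total viable count (TVC) will be obtained and expressed as colony forming units".
- **Elsewhere.** No section plans a selective medium, identification of organisms or a molecular assay. No section defines cariogenic bacteria or argues that the total count is a surrogate for them. Research Limitations does not raise the point.

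**The concern.** The objective names one quantity and the laboratory procedure measures another. A total count includes every organism that grows on this medium under these conditions, cariogenic or not. If the methods leave different proportions of cariogenic organisms in the cavity, a difference in total count can overstate, understate or even reverse the difference in cariogenic count.

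This affects one of the trial's three objectives. If the plan is followed exactly and the result is reported in the words of Objective 1, the trial will claim an organism-specific effect that it never measured.

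**Working it through.** **No figure to reproduce.** The plan gives no number for the bacterial outcome. Its sample size rests on an anxiety score (FLACC), and this point does not depend on it.

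**Step 1: objective against measurement.** Objective 1 targets cariogenic bacteria. Clinical Procedures yields total CFU per ml on one blood agar, in air, at 35°C, over 24 hours. No step in between separates cariogenic organisms from the rest. That the assay is non-selective is an inference from this description; the plan does not use the word.

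**Step 2: when the total would be enough.** For any two methods A and B, after removal:

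cariogenic ratio B/A = (total B / total A) × (share B / share A)

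The total-count ratio equals the cariogenic ratio only if the shares are equal. The same holds for fold reductions from baseline if baseline shares are balanced, which randomisation provides on average.

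**Step 3: bounds under assumed shares.** The documents give no shares, so the ranges below are assumptions. Each extreme puts one method at the top of the range and the other at the bottom. With equal total counts (ratio 1):

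| Assumed range of share | Lowest ratio | Highest ratio | log10, either way |
|---|---|---|---|
| Equal shares | 1 | 1 | 0 |
| 20–40% | 0.20/0.40 = 0.5 | 0.40/0.20 = 2 | 0.30 |
| 10–50% | 0.10/0.50 = 0.2 | 0.50/0.10 = 5 | 0.70 |
| 5–80% | 0.05/0.80 = 0.0625 | 0.80/0.05 = 16 | 1.20 |

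If shares may lie anywhere within 10–50%, a total-count difference of less than 5-fold (0.70 log10) does not fix even the direction of the cariogenic difference. A constructed reversal: total B/A = 2, with shares of 40% in A and 10% in B, gives 2 × 0.10/0.40 = 0.5.

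**Step 4: a second illustration, within one method.** Let f be the cariogenic share at baseline, and rC and rN the log10 reductions in cariogenic and other organisms. Then:

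log10 reduction in total = −log10(f × 10^−rC + (1 − f) × 10^−rN)

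- Cariogenic organisms unchanged, others down 2 log10. At f = 5%: −log10(0.05 + 0.95 × 0.01) = 1.23. At f = 50%: −log10(0.50 + 0.50 × 0.01) = 0.30.
- Cariogenic organisms down 2 log10, others unchanged. At f = 5%: −log10(0.05 × 0.01 + 0.95) = 0.02. At f = 50%: 0.30.
- At f = 90%, the two cases give 0.05 and 0.96, so the total follows the cariogenic part only when that part dominates the count.

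**Step 5: do the documents support equal shares?** They do not address it, and they give some reason not to take it for granted. The introduction says drilling removes affected as well as infected dentin, while chemo-mechanical removal is selective. Figure 2 lists chloramines in Carie-Care and, in its Papacárie entry, describes chloramine as antibiotic and disinfecting. Importance of the Research reports a manufacturer's claim of enhanced antibacterial ability for BRIX3000. None of this shows that shares differ; it shows only that equality is an assumption.

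**The case against.** The strongest reply is that the conflict is confined to one phrase. The protocol states no conclusion about cariogenic bacteria. The hypothesis and Expected Findings speak of efficacy, and Clinical Procedures already ties that word to the samples that end in the total count. Read that way, hypothesis and measurement agree. This stands: the fault lies in the wording of Objective 1, and the tie only needs to be stated in the hypothesis itself.

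The phrase may also be loose shorthand for bacteria recovered from the lesion. The lesion surface is rinsed with saline to limit plaque contamination before sampling, which fits that reading. But the plan never defines the term, and the rinse does not make the count specific to cariogenic organisms.

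The numerical bounds rest entirely on assumed shares and on extreme pairings. Comparing two teeth in the same child also makes very different baseline shares less plausible, though it does not rule out different shares after removal. This stands too: the figures show that a discrepancy is possible, not that one is likely.

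Finally, the equipment list names only one culture medium, but it also omits the colony counter and the vortexing equipment that the procedure needs. It is not a full laboratory inventory, so the point rests on Clinical Procedures.

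**Conclusion.** The point holds as a mismatch between Objective 1 and what is counted. A comparison of total aerobic viable count is supported. An inference specific to cariogenic bacteria is not, unless the cariogenic share of the count is the same across methods. The size is unknown: it is nil under equal shares, and with assumed shares within 10–50% it is at most a factor of 5 either way.

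Three stronger readings are tempting, and the documents support none of them:

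- **That the microbiological comparison is invalid.** All methods share the same assay and allocation is randomised, so the comparison of total counts stands.
- **That the trial's conclusion is wrong, or that the methods do leave different shares.** The protocol contains no results or conclusion, and no shares are given.
- **That the assay is too coarse to detect post-removal bacteria.** The dilution sentence, "The samples will be then regularly watered to obtain a 10^4", is unclear. Dilution, detection limit and zero counts are separate matters for clarification and not part of this point.

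**What to change.** Reword Objective 1, and the conclusion that will answer it, to total aerobic viable count. State in the hypothesis that efficacy means this count. Add to Research Limitations that the count is not specific to cariogenic organisms. This costs a few words and changes no procedure; the downside is a narrower claim.

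If the sponsor wants to keep the cariogenic claim, the target organisms should be named in advance and measured with a selective medium or an identification step on both samples from every tooth. This is optional and needs real laboratory work. There are 120 teeth × 2 samples = 240 samples, so one or two selective media mean 240 to 480 extra plates at one plate per sample per medium. That figure excludes replicates and identification work. The reference list already includes a study of primary-tooth dentine that, by its title, examined reduction of named organisms, so the option is a recognisable one. It would have to be arranged before samples are processed.

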- Primary molars with mobile teeth, arrested caries, restored teeth, non-vital teeth, no carious lesion, presence of developmental defects and non-restorable teeth.
- Patients on any antibiotic regimen either on the day of treatment or for at least 2 weeks prior to the study.
- Patients allergic to Latex.
- Radiographic evidence of external or internal root resorption, furcal or periapical radiolucency.
- Primary molars with more than half of the root length resorbed.
- Children who did not attend and complete the second session of treatment.
- Not approving to sign the consent.

Sample Size Calculation:

The sample size was measured using G power analysis for calculating estimated sample size.

Based on the results of Bohari et al. 2012, it was found that 30 subjects per group were required

to detect a statistically significant difference between the two groups anxiety score (FLACC) with a power of 95% at the significance level of 0.05.

The study group will be consisted of 120 primary molars with bilateral design from 60 children aged 4-9 years without sex predilection. The included teeth will be assigned randomly into one of the following groups according to the decay removal technique that will be utilized using two-arm parallel groups with split-mouth design:

The control group (A): (n=60) primary molars will be subjected to removal of caries using a conventional drilling method using carbide dental burs.

The test group (B): (n=30) primary molars will be subjected to removal of caries using a chemo-mechanical agent (Brix3000[®], Brix Medical Science, Carcarañá-Santa Fe, Argentina).

The test group (C): (n=30) primary molars will be subjected to removal of caries using a chemo-mechanical agent Carie-Care[™], Uni-Biotech Pharmaceuticals Private Limited, Chennai, India in collaboration with Vittal Mallya Scientific Research Foundation).

Armamentarium & Equipment

- 1) Basic dental examination Kit
- 2) Restorative kit
- 3) Brix3000[®] “Brix Medical Science, Carcarañá-Santa Fe, Argentina”
- 4) Carie-Care[™] “Uni-Biotech Pharmaceuticals Private Limited, Chennai, India in collaboration with Vittal Mallya Scientific Research Foundation”.
- 5) Dental bur “Low-Speed Tungsten Carbide round bur US-NO 1-8, Meisinger, USA. L.L.C., [name]; High-Speed Diamond round medium size 08-018, Meisinger, USA. L.L.C., [name]”

- 6) Rubber dam kit.
- 7) Sterile vial.
- 8) Bacteriological incubator

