Caries removal will be carried out using a sterile Tungsten carbide round bur “US-NO 1-8, Meisinger, USA. L.L.C., [name]” on micromotor handpiece at slow speed (6000-8000 rpm) without water spray. If necessary, undermined enamel will be removed with rotary cutting bur in high speed to enlarge the cavity and provide an adequate access to remove all softened dentin tissue beneath. After caries removal, dentin will be considered caries free utilizing visual and tactile clinical criteria.

The Experimental Group (BRIX-3000): Caries removal using “chemo-mechanical agent” (Brix3000[®])

According to manufacturer's instructions, the restorative procedure will be performed without anesthesia under partial isolation with cotton rolls according to the principles of “Atraumatic Restorative Treatment (ART)”. Then, the papain-based gel BRIX 3000[®] will be applied to the cavity with double-ended dental spoon excavator (Size #2, #3, #4; Nordan Manufacturing Inc., [name]) leaving it to act for 2 minutes. After 1 minute, the formation of oxygen will be observed and the gel will be turned from translucent green color to cloudy. Then, the infected tissues will be removed through curettage by dental spoon excavator with pendulum movement without pressure, first at the surrounding walls followed by pulp wall removal. After the gel removal, the cavity will be rinsed with water and dried using mild air blow. The cavity will then be evaluated for any residual softened dentin tissue. The procedure could be repeated by applying BRIX3000[®] as many times as required to remove all of the infected carious tissue. The presence of healthy dentin will be confirmed when (the gel is no longer changed in color and turned turbid. The cavity will be examined according to visual “absence of any discoloration” and tactile “smooth passage of explorer and absence of a catch or tug back sensation” clinical criteria using a dental explorer. Caries will be regarded to be totally removed when the explorer did not stick in dentin and gave no tug back sensation. If necessary, undermined enamel will be removed with rotary cutting bur in high speed “round medium diamond bur size 08-018, Meisinger, USA. L.L.C., [name]” to enlarge the cavity and provide an adequate access to remove all softened dentin tissue beneath.

The Experimental Group (Carie-Care): Caries removal using “chemo-mechanical agent” (Carie-CareTM)

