The carious cavity will be treated with Carie-Care™ “Uni-Biotech Pharmaceuticals Private Limited, Chennai, India in collaboration with Vittal Mallya Scientific Research Foundation”. Following the instructions of the manufacturer, the Carie-Care™ gel will be brought to room temperature. The gel will be left in the carious lesion for 60 seconds. At that time, the appearance of the gel will be changed from translucent into cloudy. Then the gel will be removed with moistened cotton pellet and softened carious dentin will be scrapped off using spoon excavator ((Size #2, #3, #4; Nordent Manufacturing Inc., [name]). The process will be redone till consecutive administration of the gel was unsuccessful to turn into cloudy. Decay removal will be verified by probing with dental explorer (visual-tactile clinical criteria).

Statistical Analysis

The statistical assessment will be carried out using Statistical Package for Social Sciences (SPSS, V.20, IBM; Armonk, NY, USA). Analysis of data will be done through measuring *p*-value to determine statistical significance. The level of significance will be set at 0.05 (*p*-value of less than 0.05 was considered statistically significant). Various statistical methods will be used for measuring *p*-value depending whether the data will be normally distributed (parametric) or not normally distributed (non-parametric). For normally distributed data, paired sample t-test and independent sample t-test will be used. For non-normally distributed data, Wilcoxon signed rank test and Mann Whitney U test will be used.

Wong-Baker FACES® Pain Rating Scale

[figure not shown]

Figure 4: Wong-Baker FACES® Pain Rating Scale.

RESEARCH LIMITATIONS

Although, the chemo-mechanical methods cannot eliminate the dental caries completely, it tends to follow the principles of minimal intervention dentistry approaches. The generalization of results is one of the expected limitations of this research.

STRUCTURE OF THE RESEARCH

The research will be divided into several chapters:

- Chapter 1 will represent the introductory note on the state of dental caries among children and treatment approaches that are extensively used by the dentists including different chemo-mechanical agents used.
- Chapter 2 will present the literature review for the study.

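### The protocol gives opposite anaesthesia and isolation rules for the Brix3000 arm; if the arm-specific rule is followed, both Brix3000 pain contrasts are confounded with anaesthesia

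*Combined protocol and SAP*

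**What the plan says.** The list of treatment steps under Clinical Procedures sets two conditions common to every arm: "Local anesthesia will be used for all groups" and "Rubber dam isolation will be used for all groups". Caries removal by one of the three techniques is the next step.

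The Brix3000 description that follows begins: "According to manufacturer's instructions, the restorative procedure will be performed without anesthesia under partial isolation with cotton rolls". It cites the principles of atraumatic restorative treatment, and its next sentence moves straight on to applying the gel. The drilling and Carie-Care descriptions contain no exception on anaesthesia or isolation, so the common rule applies to them.

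The third research objective is "To compare the pain experienced by children during dental treatment with the chemo-mechanical method" against the conventional method, and the null hypothesis covers pain across all three techniques. The Wong-Baker FACES scale is to be used "To assess the pain experienced throughout caries removal in all groups". For normally distributed data, Statistical Analysis says "paired sample t-test and independent sample t-test will be used", with the Wilcoxon and Mann-Whitney tests otherwise. It plans no adjustment and does not mention anaesthesia.

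**The concern.** The two instructions cannot both be carried out on a Brix3000 tooth, and no visible text ranks them or calls Brix3000 an exception.

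Anaesthesia bears directly on the pain outcome. The Literature Review itself reports the argument that chemo-mechanical removal spares children pain and anxiety because no injection is needed. In the other direction, the Brix3000 procedure allows a high-speed bur where enamel is undermined, and that could hurt more without anaesthesia. A difference between arms could therefore push the Brix3000 pain score either way.

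Expected Findings anticipates less pain with Brix3000 than with both Carie-Care and drilling. Those are the two contrasts at risk.

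**Working it through.** **Inputs.** From Sample Size Calculation: 60 children and 120 molars (60 drilled, 30 Brix3000, 30 Carie-Care). Each child contributes one drilled tooth and one gel tooth, giving 30 Brix3000/drill pairs and 30 Carie-Care/drill pairs. Brix3000 and Carie-Care are compared between children. The anaesthesia rules are those set out above.

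**The plan's own figure.** The 30 per group, at 95% power and a 0.05 level on the FLACC score, cannot be reproduced forward because no effect size, standard deviation or sidedness is given. Back-solved for two independent groups, two-sided, by the normal approximation: d = (1.960 + 1.645) × √(2/30) = 0.93. The t-test gives 0.95. The point made here does not depend on this figure.

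**Teeth and pairs under each reading.**

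| | Common rule followed | Brix3000 rule followed |
|---|---|---|
| Brix3000 teeth without anaesthesia | 0/30 | 30/30 |
| Carie-Care teeth without anaesthesia | 0/30 | 0/30 |
| Drilled teeth without anaesthesia | 0/60 | 0/60 |
| Brix3000/drill pairs that differ in anaesthesia | 0/30 | 30/30 |
| Carie-Care/drill pairs that differ in anaesthesia | 0/30 | 0/30 |
| Pain contrasts confounded | 0 of 3 | 2 of 3 |

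**Can analysis repair it?** Under the Brix3000 rule, anaesthesia = 1 − (Brix3000 indicator). A model with intercept, Brix3000, Carie-Care and anaesthesia has 4 columns but rank 3, so the gel and anaesthesia effects are not separately estimable. Randomisation does not help, because anaesthesia would be fixed by the allocation.

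**Mixed practice.** Let f be the share of Brix3000 teeth treated without anaesthesia (0 to 1), and d_a the mean effect on the pain score of omitting it. The bias in each Brix3000 contrast is f × d_a. It is zero at f = 0 and equals d_a at f = 1. The documents give neither f nor d_a.

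**Illustration with assumed shifts.** Suppose there is no true difference between techniques, f = 1, and anaesthesia alone shifts pain by b standard deviations. The chance of a significant result at two-sided 0.05 is then:

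| Assumed b | Brix3000 vs Carie-Care, 30 vs 30 | Brix3000 vs drill, 30 pairs, assumed within-child correlation 0.5 |
|---|---|---|
| 0.2 | 12% | 18.5% |
| 0.5 | 48% | 75% |
| 0.8 | 86% | 99% |

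The noncentrality is b × √(30/2) for the independent test and b × √30 for the paired test; with correlation 0.5, the standard deviation of a difference equals that of a single score. The reverse can also happen. If the true between-group benefit were 0.95 SD, an opposing shift of 0.5 SD would leave 0.45 SD and cut power from 95% to about 40%. The values of b and the correlation are assumptions, not figures from the documents.

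**The case against.** The harm is conditional. The Brix3000 sentence is prefaced as manufacturer's wording and sits inside a step that comes after anaesthesia and rubber dam, so it may be carried-over product text that nobody meant to apply. If so, no pain contrast is biased. That stands, and it limits the confounding claim to the case where the sentence is followed. It does not remove the contradiction. The sentence opens the arm's own procedure, and a specific instruction is often read as overriding a general one.

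A second defence is that avoiding the injection is part of what chemo-mechanical removal offers, as the Literature Review suggests, so Brix3000 against drilling would be a fair comparison of treatment packages. That is reasonable for this one contrast, if it is declared. It does not rescue Brix3000 against Carie-Care, where one gel would be used without anaesthesia and the other with it.

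The equipment list does not decide the matter. It includes "Rubber dam kit" and no cotton rolls, but 90 of the 120 teeth would need a dam under either reading. It names no anaesthetic at all, and it also omits items plainly in use, such as spoon excavators. The flow diagram (Figure 3) and the consent pages were not available, so the absence of a reconciling statement refers to the visible text.

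The effect shown is on pain only. The stopwatch starts when caries removal starts, so giving the injection is outside the timed interval. Different isolation could affect the bacterial count after removal, but the documents give no size for this. In all groups "the cavity will be washed with sterile normal saline (5 mL) and dried with a sterile cotton pellet" before the second sample, which may reduce it.

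**Conclusion.** The concern holds. The contradiction on anaesthesia and isolation is certain from the text. Its consequence depends on which sentence is followed: no confounding under the common rule, and under the Brix3000 rule two of the three pairwise pain contrasts cannot be attributed to the gel. Carie-Care against drilling is sound under both. This rests on one assumption, that silence in the drilling and Carie-Care descriptions leaves the common rule in force for them, which is the natural reading. The size and direction of any bias cannot be stated from the documents. This is an error in the written plan rather than a missing detail, because a stated instruction, followed literally, would undermine a stated objective. It should be corrected before children are treated.

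**What to change.** Apply one anaesthesia and isolation rule to all three arms. The simplest way is to keep the common steps (local anaesthesia and rubber dam throughout) and delete the clause on no anaesthesia and cotton rolls from the Brix3000 procedure. Record the anaesthesia and isolation actually used for each tooth, so that departures can be seen and reported.

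If the investigators deliberately want Brix3000 without anaesthesia, they should declare the exception and reword the third objective and its conclusion as a comparison of treatment packages. They should also accept that Brix3000 against Carie-Care will not isolate the gel.

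The cost is one protocol clarification, possibly notified to the ethics committee, a check that the parental consent information matches the chosen rule, and the added per-tooth record. No extra patients are needed. The trade-off is that Brix3000 would be tested under anaesthesia and rubber dam, contrary to the manufacturer's instructions as reported in the protocol. Anaesthesia in every arm may also narrow pain differences during removal, though the documents give no figure for this.
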